9.2.2 Serious Adverse Events

Any AE is considered "serious" if it:

- results in death (note: death is an outcome, not an event);
- is life-threatening; (note: the term "life-threatening" refers to an event in which the patient was at immediate risk of death at the time of the event; it does not refer to an event which could hypothetically have caused a death had it been more severe);
- requires in-patient hospitalization or prolongs an existing hospitalization;
- results in persistent or significant disability/incapacity;
- is a congenital anomaly/birth defect;
- is an important medical event, i.e., refers to an event that may not result in death, be lifethreatening, or require hospitalization but may be considered as serious when, based upon appropriate medical judgment, may jeopardize the patient, and may require medical or surgical intervention to prevent one of the outcomes listed in this definition above.

The following reasons for hospitalization are exempted from being reported:

- elective hospitalizations for surgical procedures that are a result of a patient's pre-existing condition(s) which have not worsened during the study;
- hospitalization requested for emapalumab infusion and study visits (including a possible hospital stay overnight, if due to logistic convenience);
- post-HSCT hospitalization as a measure of caution in this fragile population, to investigate a clinical sign or symptom (e.g. fever), provided that the hospital stay has a duration of less than 72 hours and does not result in any confirmed new diagnosis (e.g., negative search of infection in

presence of fever which resolves with symptomatic measures); in this case the sign will be recorded as an AE.

For the initial SAE report, the Investigator should report all available case details concerning the patient and the event, using the Swedish Orphan Biovitrum AG SAE reporting form within 24 hours of awareness.

Swedish Orphan Biovitrum AG contact information for SAE reporting:

E-mail: [contact]

Relevant follow-up information on SAEs should be forwarded to Swedish Orphan Biovitrum AG as soon as it becomes available. In addition, the Investigator must be available to answer without delay any request for follow-up information or questions that Swedish Orphan Biovitrum AG may have regarding the SAE.

All SAEs will be recorded on the appropriate page of the eCRF. They will be reviewed, evaluated and followed up until the event resolves or is considered stable by a study physician.

If either the Sponsor or Investigator believes that the event is serious, the event must be considered serious and evaluated by the Sponsor for expedited reporting.

9.2.3 SUSAR reporting

Suspected Unexpected Serious Adverse Reactions (SUSARs) are SAEs that are both:

- related, i.e., there must be a certain degree of probability that the event is a harmful and undesirable reaction to the IMP under investigation, regardless of the administered dose
- unexpected, i.e., the event is not listed as an expected serious adverse reaction in the Reference Safety Information (RSI) of the Investigator's Brochure

All SUSARs will reported by the sponsor to relevant Health Authorities, Ethics Committees (ECs)/Institutional Review Boards (IRBs)/Research Ethics Boards (REB) and investigators as per applicable regulations.

Under the USA 21 Code of Federal Regulation (CFR) 312.32(c), the Sponsor (directly or through a delegated third party) is required to notify the Food and Drug Administration (FDA) and all participating Investigators in an Investigational New Drug (IND) safety report (i.e., 7- or 15-day expedited report) of potentially serious risks from clinical trials or any other source as soon as possible, but no later than 15 calendar days after the Sponsor receives the safety information and determines that the information qualifies for reporting.

Investigators in the USA are required to promptly report to the IRB all unanticipated problems involving risk to human subjects or others, including AEs that should be considered unanticipated problems (21 CFR 312.66), such as IND safety reports.

In countries other than the USA, the Sponsor will promptly evaluate all SAEs and against cumulative product experience to identify and expeditiously communicate possible new safety findings to investigators, IRBs, ECs, REBs and applicable health authorities based on applicable legislation.

Swedish Orphan Biovitrum AG will also report all SUSARs to the EMA's EudraVigilance database within 15 days, as well as to the relevant National Competent Authorities when required. Fatal and life-threatening SUSARs will be reported within 7 calendar days, with another 8 days for completion of the report.

9.2.4 Managing Abnormal Laboratory Test Values

All laboratory tests (hematology, coagulation, blood chemistry) will be captured in the database from the local laboratory.

Laboratory test abnormalities must be considered as AEs and recorded on specific AE pages of the CRF only if they:

- require specific intervention for correction, or
- lead to a change in study medication (e.g., dose modification, interruption or permanent discontinuation), or
- qualify as grade 4 severity as per modified WHO toxicity scale

If a laboratory test abnormality leads to a new clinical diagnosis, the new clinical diagnosis should be reported as an AE rather than the laboratory abnormality.

Laboratory test abnormality that qualifies as an AE as per the definition above, will follow the AE/SAE reporting process described in this section.

Laboratory abnormalities which are considered to be part of HLH signs and symptoms (see Section 9.2.1) will not be reported as AEs. If laboratory abnormalities are indicative of an HLH reactivation or worsening, the reactivation or worsening of HLH will be reported as the AE, and not the laboratory abnormalities themselves.

9.3 FOLLOW-UP OF SAFETY PARAMETERS

9.3.1 Follow-up of Adverse Events

Adverse events should be followed up to resolution or stabilization or until they return to baseline status (in the event of an exacerbation of a pre-existing condition).

For AEs still ongoing at study completion or withdrawal, where return to baseline status or stabilization cannot be established, an explanation should be recorded.

9.3.2 Follow-up of Abnormal Laboratory Test Values

Abnormal laboratory findings that qualify as AEs should be followed-up as per Section 9.3.1.

9.3.3 Pregnancy

Occurrence of pregnancy in a study participant will require discontinuation of the IMP and entry into the study follow-up period.

Pregnancies, including pregnancies of female partners of male study participants must be reported to Swedish Orphan Biovitrum AG within 24 hours of awareness on the Swedish Orphan Biovitrum AG Pregnancy form.

A pregnancy must be followed until its conclusion. Any AE associated with the pregnancy occurring during the follow-up period after study treatment discontinuation must be reported in the eCRF. Any SAE occurring during the pregnancy must be reported on an SAE form as described in Section 9.2.2.

9.4 BENEFIT/RISK MANAGEMENT

9.4.1 Safety Surveillance Management

HLH is a rare disease, and experience gathered from previous exposure of patients to emapalumab is still limited. It is therefore required that patients are monitored during and for 2 hours after each infusion of emapalumab, and that infusions are administered under medical supervision within a unit having emergency equipment.

The iDMC will ensure that any emergent safety concern will be assessed in a timely manner and appropriate measure taken for the patients, if relevant. Moreover, iDMC will be specifically tasked with regular assessment of the extent of benefit and fatal events prior to transplant in the treatment-naïve subgroup of patients.

9.4.2 General Benefit/Risk Considerations

9.4.2.1 Potential benefits

Based on evidence available from comprehensive analysis of the NI-0501-04 and NI-0501-05 studies that formed the basis of the BLA and MAA submissions, emapalumab administration has shown the potential to improve or resolve relevant clinical and laboratory abnormalities of HLH. Emapalumab demonstrated a statistically significant and clinically relevant reduction in HLH disease activity, assessed through objective clinical and laboratory parameters, in 64.7% of patients. Response occurred early during treatment and was generally sustained. The reduction in HLH disease activity was sustained and was associated with an overall survival benefit that persisted following HSCT. The observed treatment effect was consistent across all efficacy endpoints. Emapalumab was well tolerated in doses up to 10 mg/kg and no off-target toxicity has been identified. Emapalumab treatment could be continued safely and effectively beyond 8 weeks in patients for whom the search for a donor was longer than expected.

The response to emapalumab seems independent of:

- the presence and type of causative mutations
- the presence and type of an infectious trigger

On 20 November 2018, emapalumab was approved by the FDA "for the treatment of adult and pediatric (newborn and older) patients with primary hemophagocytic lymphohistiocytosis (HLH) with refractory, recurrent or progressive disease or intolerance with conventional HLH therapy".

For more details, refer to the latest Investigator's Brochure (currently version 10.0, dated 24 January 2020).

9.4.2.2 Risks

Infusion-related reactions

Infusion-related reactions (IRRs) are commonly associated with monoclonal antibody infusions and are defined as signs or symptoms with a temporal relationship to the administration of an infusion and assessed as related, typically occurring soon after the start of the infusion, although symptoms may be delayed for up to 24h. They might be limited (skin reaction) or systemic.

After more than 1000 infusions administered to HLH patients up to the dose of 10 mg/kg, no anaphylactic/anaphylactoid or other significant reactions were observed with emapalumab. IRRs were mainly transient skin reactions observed during and shortly after emapalumab infusions (corresponding

to less than 2% of the infusions performed). They resolved spontaneously and did not lead to emapalumab permanent discontinuation.

From the clinical experience to date, the risk of IRRs associated with emapalumab treatment seems to be very low. However, the infusion should be performed under medical supervision with monitoring of vital signs during and for 2 hours after emapalumab infusion as outline in Section 8.

Immunogenicity

Occurrence of ADAs inactivating therapeutic effects of the treatment and, in rare cases, inducing adverse reactions, is a potential risk associated with the administration of monoclonal antibodies (mAbs). As of 24 August 2019, treatment-emergent ADAs were detected in:

- 1 out of 14 healthy subjects participating in study NI-0501-03; a low titer of ADAs was measured at the last follow-up visit (at week 44 post-emapalumab administration
- 3 out of 45 patients treated in the context of NI-0501-04/05 studies
- 1 patient treated in compassionate use developed transient ADAs

No AEs, including decreased efficacy, attributable to antibodies have occurred in these patients. In addition, in ongoing studies in patients with sJIA/MAS (NI-0501-06, N=8) and in patients with pHLH (NI-0501-09, N=9), no ADA were detected.

Drug-drug interactions

High IFNy production and subsequent hyper production of other cytokines during active pHLH might downregulate cytochrome P450 enzymes (CYPs), resulting in suppression of CYP isoenzymes activity during active disease. Anti-cytokine mAbs have the potential to restore CYP activity back to normal, through neutralization of the pro-inflammatory cytokine which is targeted by the antibody and the ensuing reduction in inflammation (Morgan, 2009). The restoration of CYP activity may therefore alter the elimination of concomitant medications metabolized by these CYPs. During the clinical trials with emapalumab, no events of Therapeutic Protein-Drug Interactions (TP-DI) were reported in pHLH patients.

Infections

The impact on the immune defense caused by the neutralization of IFNγ is known from patients with inborn errors of the IL-12/23-IFN-γ circuit, particularly patients with complete or partial IFNγ receptor (R) deficiency, and patients developing neutralizing auto anti-IFNγ antibodies. Patients with IFNγ R deficiency are prone to develop mycobacterial infections and, although to a lesser extent, *Salmonella* infections (Dorman 2000, Jouanguy 1997). The mean age of the first environmental mycobacterial infection is 3.1 and 13.4 years in patients with complete and partial deficiency, respectively (Remus 2001).

No systematic prophylaxis is recommended in these patients. If an infection occurs, appropriate antibiotic therapy based on sensitivity of isolated species is prescribed.

Individuals with anti-IFNy auto-antibodies are also susceptible to develop mycobacterial infections (for the vast majority atypical mycobacterial infections), but also opportunistic infections (e.g., caused by *Histoplasma capsulatum, Salmonella*, HZV) (Browne 2012).

Toxicological studies carried out with emapalumab have shown an increased susceptibility to enteral pathogen infections in monkeys having received emapalumab, when the enteral pathogen was present in the intestinal tract prior to emapalumab administration. Therefore, presence of infections due to *Shigella*, *Salmonella* and *Campylobacter* pathogens is part of the exclusion criteria.

As to the development of infections caused by pathogens known to be favored by the absence of IFNy biological activity, a reactivation of HZV (which resolved after a normal course with no sequelae) was observed in one healthy volunteer, at a dose of 3 mg/kg; and one HLH patient enrolled in the NI-0501-04 study developed a disseminated histoplasmosis which resulted in treatment discontinuation. This infection resolved with adequate antifungal therapy, even though emapalumab was still at detectable concentrations in blood.

Other infections reported during or after administration of emapalumab are the same ones commonly observed in immunocompromised patients or are the same ones described in pediatric populations (seasonal viral infections). Patients with active infections (except for the exclusionary ones) were enrolled and treated in the study. The presence of active infections did not lead to the discontinuation or dose decrease of emapalumab treatment, and infections resolved on study drug when treated appropriately and not associated with a refractory disease status. Severe or serious infections were generally reported in patients with previous recent significant exposure to immunosuppressive treatments as they added an additional risk factor for infection development. Importantly, emapalumab treatment has not been associated with myelosuppression.

Active infections, as per patient's clinical presentation, must be carefully followed over time, including quantitative monitoring (e.g. viral loads, antigenemia, antigenuria), when relevant.

For more details refer to the latest Investigator's Brochure (currently version 10.0, dated 24 January 2020).

9.4.2.3 Risk minimization measures

In view of the above reported considerations, the benefit/risk profile of emapalumab in children diagnosed with pHLH is considered to be favorable.

Specific measures are implemented to minimize the potential risks described above as follows:

- As per eligibility criteria, patients with evidence of active Mycobacteria, Histoplasma, Shigella, Salmonella, Campylobacter or Leishmania infections, or latent tuberculosis will not be included in the study (for details see Section 4.1.2). Patients who received live or attenuated live vaccine within 6 weeks prior to screening are excluded from the studies with emapalumab.
- Monitoring of IRRs: infusions will be performed under medical supervision to immediately identify the occurrence of any IRRs. Each of the specialized centers will have personnel adequately trained in IRR management.
- Prophylaxis for HZV for all patients, and tuberculosis for a defined subpopulation (see Section 6.2), is required per protocol.
- Occurrence of emerging infections and evolution of pre-existing infections are monitored
 through regular physical examination and laboratory testing, including detection of
 tuberculosis. Ad hoc search for infections will be performed based on signs and symptoms
 indicating a suspicion of infection. Empirical antibiotherapy will be introduced when deemed
 appropriate, and proper monitoring of active pre-existing infections or emerging infections
 will be conducted.

10 STOPPING RULES

10.1 AT PATIENT LEVEL

10.1.1 Decision to Slow Down or Stop Emapalumab Infusion due to Systemic Reaction

During the infusion of emapalumab, any significant change compared to pre-infusion values in vital signs, such as those listed below, should trigger appropriate immediate care:

- Sudden and sustained increase or paradoxical decrease of heart rate (duration of more than 5 minutes) compared to pre-infusion value and not linked to child's anxiety or fear;
- Sustained (an episode of more than 5 minutes duration or more than 3 episodes of shorter duration, i.e., 3 minute) oxygen desaturation (below 90%);
- Any clinical sign or complaint indicative of patient distress

The decision to interrupt the infusion might be taken by the physician in the event of any of the above mentioned occurrences.

The decision to restart the infusion will be based on the evolution of the patient's status (i.e., resolution of symptoms after appropriate symptomatic measures, e.g., oxygenation or administration of anti-histamine treatment), and upon physician's own medical judgment. The infusion will generally be restarted at a lower rate.

All changes in infusion rate will be recorded in the patient's medical chart and the eCRF each time there is a rate modification, as well as at the end time of premature or delayed termination of the infusion.

10.1.2 Local Issues During Emapalumab Infusion

Unless related to a hypersensitivity reaction, a local infusion issue such as catheter displacement, obstruction or product extravasation, will trigger the infusion of the remaining quantity through a new venous access as soon as possible. All information related to the incident will be recorded accurately in the patient's medical chart prior to being entered in the eCRF. This includes reasons, volume of IMP potentially lost (to calculate the quantity of drug infused), time at which the infusion stopped, time at which the infusion was resumed and time of end of the infusion.

To avoid this type of incident, it is preferable that a central venous access is used: this will improve patient's comfort and ensure a reliable drug administration in particular in infants and toddlers or in case of foreseen difficulties with peripheral venous access.

10.1.3 Decision to Discontinue Treatment or to Withdraw from the Study

The Investigator can decide at any time during the study to discontinue the treatment for an individual patient based on his/her own medical judgment, taking into account the individual benefit/risk ratio for his/her patient. After treatment discontinuation (for any reason), the patient will continue in the study for a long-term follow-up.

In addition, the patient (or their legal representative) can decide at any time to withdraw from the study.

The reason for premature treatment discontinuation or study withdrawal should be documented in the patient's chart and shared with the Sponsor.

Study NI-0501-09 NI-0501 in Primary HLH Page 66 of 92

The Investigator may request expert advice or a discussion with the Sponsor to receive additional information, if relevant prior to taking a decision; however, the ultimate decision remains the Investigator's responsibility.

In any case, the decision to withdraw or be withdrawn from the study and/or treatment will have no impact on the patient's care and on further treatments administered to him/her after withdrawal. The management of these patients is described in Section 10.3.

10.2 AT STUDY LEVEL

Recruitment may be temporarily suspended in the following situations:

- occurrence of unexpected fatal or life-threatening adverse reactions;
- emergence of severe drug reactions linked to a common cause/ risk factor at different sites

Patients already enrolled in the study should continue receiving emapalumab per protocol unless decided otherwise by the Investigator.

The suspension will allow for the analysis of the available data by the Sponsor and the iDMC.

After re-evaluation of benefit/risk, the sponsor and iDMC may recommend any of the following:

- to resume recruitment without any change;
- to implement risk minimization measures that may require protocol amendment;
- to implement conditions for study termination, e.g., next occurrence of a particular serious drug reaction

The management of patients already enrolled in the study will also be part of the iDMC recommendations.

10.3 MANAGEMENT OF TREATMENT DISCONTINUATION

All patients who discontinue emapalumab treatment will be treated according to the standard care at the site. However, it is recommended they continue in the study for long-term follow-up monitoring.

11 STATISTICAL CONSIDERATIONS AND ANALYTICAL PLAN

Full details of all statistical issues and planned statistical analyses will be specified in a separate Statistical Analysis Plan (SAP), which will be finalized prior to the locking of the study database. This section contains an overview of the planned methods of analysis.

11.1 SAMPLE SIZE

The sample size calculation is based on the primary efficacy endpoint of "Overall Response".

Assuming an Overall Response Rate of 65%, a minimum of 34 treated patients is required to show a significant improvement above 40% with 85% power using an exact binomial test at a one-sided significance level of 2.5%. A drop-out rate of 20% may be expected, hence a total maximum of 41 patients may be enrolled.

Due to the rarity of pHLH, recruitment is competitive across all European and NA sites in order to gather data in a reasonable timeframe.

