Study Population:	Male and female pHLH patients, from birth up to and including 18 years at diagnosis of HLH. Patients can be naïve to HLH treatment or may have received conventional HLH therapy without having obtained a satisfactory response according to the treating physician, or having shown signs of intolerance to previous HLH therapy.
Inclusion Criteria:	 Of note, the enrolment of patients will continue until emapalumab is commercially available for a given indication, or until sample size is reached, whichever comes first; thus, US enrolment will be limited to treatment-naïve patients. Male and female pHLH

patients, from birth up to and including 18 years at diagnosis of HLH.

- A molecular diagnosis or familial history consistent with pHLH or fulfilment of HLH-2004 diagnostic criteria, i.e., five of the eight criteria below:
 - Fever
 - Splenomegaly
 - Cytopenias affecting 2 of 3 lineages in the peripheral blood (hemoglobin <90 g/L; platelets <100 x 10⁹/L; neutrophils <1 x 10⁹/L)
 - Hypertriglyceridemia (fasting triglycerides ≥3 mmol/L or ≥265 mg/dL) and/or hypofibrinogenemia (≤1.5 g/L)
 - Hemophagocytosis in bone marrow, spleen or lymph nodes, with no evidence of malignancy
 - Low or absent natural killer (NK)-cell activity
 - Ferritin ≥500 μg/L
 - Soluble CD25 (sCD25, i.e., soluble IL-2 receptor) ≥2400 U/mL
- 3. Presence of active HLH disease as assessed by the treating physician.
- 4. Patients having already received conventional HLH therapy must fulfil one of the following criteria as assessed by the treating physician:
 - Having not responded
 - Having not achieved a satisfactory response or worsened
 - Having reactivated
 - Showing intolerance to previous conventional treatment of HLH.

At the time of enrolment, eligible patients might still be receiving treatment (induction or maintenance) or might have already discontinued it.

- Informed consent signed by the patient (as required by local law), or by the patient's legally authorized representative(s) with the assent of patients who are legally capable of providing it, as applicable.
- 6. Having received guidance on contraception for both male and female patients sexually active and having reached puberty.

Females of child-bearing potential require use of highly effective contraceptive measures (failure rate of less than 1% per year) from Screening until 6 months after receiving last dose of the study drug. Highly effective contraceptive measures include:

- o Sexual abstinence

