Unsatisfactory HLH control is defined as follows:

- patients who have not achieved or maintained a disease control and general conditions that would allow to proceed to transplant
- patients who present a clinically relevant HLH worsening.

If an additional HLH treatment is needed, etoposide is the drug of choice, unless there is evidence indicating that an alternative agent should be selected.

Sample Size:

The sample size calculation is based on the primary efficacy endpoint of 'Overall Response'. Assuming an Overall Response Rate of 65%, a

minimum of 34 patients is required to show a significant improvement above 40% with 85% power using an exact binomial test at a one-sided significance level of 2.5%. A drop-out rate of 20% may be expected, hence a total maximum of 41 patients may be enrolled.

Number of Sites:

It is estimated that approximately 13 sites in North America and approximately 15 sites in Europe will participate in this study.

Study Duration and Study End Definition:

After treatment completion or treatment discontinuation (for any reason), patients will continue in the study for a long-term follow-up. End of the study is defined as last patient last visit at 1 year after either

End of the study is defined as last patient last visit at 1 year after either HSCT or last emapalumab infusion (as applicable). Survival data obtained at 2 year and 3 year follow-up will be analyzed separately.

Study Surveillance, Safety Reporting and Stopping Rules:

Infusions should be performed under medical supervision and monitored as per local standard of care based on patient's conditions, with a minimum requirement of monitoring blood pressure, body temperature, heart rate and oxygen saturation during the administration of emapalumab, and up to 2 hours after the end of the infusion.

Adverse events (AEs) will be recorded from the date of the informed consent form (ICF) signature until serum levels of emapalumab are no longer detectable, except for the following:

- Common HLH signs and symptoms (e.g. anemia, neutropenia, thrombocytopenia, hepatosplenomegaly) will not be reported as separate events unless clearly attributed to a cause different from HLH; however, reactivation or worsening of HLH from start of treatment with emapalumab will be reported as AE;

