11.2.1 All Treated Analysis Set

The All Treated Analysis Set will include all patients who receive any part of an infusion of study drug, and will be as the Primary Efficacy and Safety Analysis Set.

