11.3.1 Efficacy Data

The analysis of the primary endpoint, Overall Response Rate, will utilize an exact binomial test to evaluate the null hypothesis that the response rate is at most 40%. This test will be undertaken at the one-sided 0.025 level.

Time to Response, Duration of Response, and Survival time will be presented using Kaplan-Meier curves with medians calculated if available. Ninety-five percent confidence intervals will be calculated for the median for each of these endpoints.

For maintenance of response achieved any time during the study, event of interest will be the loss of response, with patients in response being censored on the day starting conditioning.

Additional endpoints based on binary outcomes including number of patients who reduce glucocorticoids by 50% or more, and number of patients able to proceed to HSCT will be converted to proportions and associated 95% confidence intervals calculated.

Statistical significance in terms of p-values will only be obtained for the primary endpoint in both the All Treated and the Evaluable analysis sets. All other endpoints will be viewed as supportive for the primary endpoint and as a consequence no formal hierarchy of endpoints will be declared.

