11.4 REPLACEMENT POLICY

11.4.1 For Patients

Additional patients will be recruited into the study if patients are withdrawn from the study for reasons other than safety or lack of efficacy to ensure a sample size of a minimum of 34 patients.

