3.2. Sample Size and Power

The sample size calculation is based on the primary efficacy endpoint of Overall Response. Assuming an Overall Response Rate of 65%, a minimum of 34 treated patients is required to show a significant improvement above 40% with 85% power using an exact binomial test at a one-sided significance level of 2.5%. A drop-out rate of 20% may be expected, hence a total maximum of 41 patients may be enrolled. Due to the rarity of pHLH, recruitment is competitive across all European and North American sites in order to gather data in a reasonable timeframe.

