8.1. Primary Efficacy Analysis

The primary efficacy endpoint is Overall Response at EOT or Week 8 (whichever occurs earlier) (Section 6.1.9.4) with imputation of missing values. The primary efficacy endpoint and its components (Complete Response, Partial Response, and HLH Improvement) will be summarized using descriptive statistics. The analysis of the primary endpoint will utilize an exact binomial test to evaluate the following hypotheses:

Ho: $R \le 40\%$ H1: R > 40%

[figure not shown]
where R is the percentage of the number of patients that achieved Overall Response in the All Treated Analysis Set divided by the total number of patients in the All Treated Analysis Set. The test will be undertaken at the one-sided 0.025 level. The 2-sided exact 95% confidence interval will be provided as well as the 95% confidence interval calculated via the Wilson score method as supportive.

This evaluation will be presented as described in Table 3.

The components of the primary efficacy endpoint (Complete Response, Partial Response, HLH Improvement and No response) will be summarized using counts and percentages at Week 8 or EOT (whichever occurs first).

Sensitivity analyses will be performed on the primary efficacy endpoint using the same test, and displayed as outlined in Table 3:

Version 2.0 Date 24-Oct-2022	AD-PR-109.02 Effective date: 17-Aug-2020)
--------------------------------	--	---

Sensitivity analysis 1: Overall Response at EOT or Week 8 (whichever occurs earlier) with deaths considered as non-responders.

Sensitivity analysis 2: Overall Response at EOT or Week 8 (whichever occurs earlier) with early withdrawal considered as non-responders.

Sensitivity analysis 3: Overall Response at EOT or Week 8 (whichever occurs earlier) with patients who receive concomitant administration of other HLH treatments considered as non-responders.

Sensitivity analysis 4: Overall Response at EOT or Week 8 (whichever occurs earlier) with deaths, early withdrawals, and patients who receive concomitant administration of other HLH treatment considered as non-responders.

Sensitivity analysis 5: Overall Response at EOT or Week 8 (whichever occurs earlier) with patients deemed as having a major protocol deviation impacting statistical analysis removed from the Evaluable Analysis Set.

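### With 34 treated patients the named exact binomial test has 82.6% power, not the stated 85%

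*Protocol*

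**What the plan says.** The sample size statement appears three times.

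- Protocol 11.1 says that "a minimum of 34 treated patients is required to show a significant improvement above 40% with 85% power using an exact binomial test", assuming a 65% overall response rate and a one-sided 2.5% level. SAP 3.2 uses the same words.
- The Protocol synopsis (Sample Size) omits the word treated: "minimum of 34 patients is required to show a significant improvement above 40% with 85% power using an exact binomial test".
- All three then add the allowance for losses, in the words of SAP 3.2: "A drop-out rate of 20% may be expected, hence a total maximum of 41 patients may be enrolled".

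The test in that statement is also the test of the primary analysis. Protocol 11.3.1 says the analysis "will utilize an exact binomial test to evaluate the null hypothesis that the response rate is at most 40" per cent, at the one-sided 0.025 level. SAP 8.1 sets out the same hypotheses and level.

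The primary denominator is the All Treated Analysis Set, which is "all patients who receive any part of an infusion of study drug" (Protocol 11.2.1). In SAP 8.1 the response rate is the number of responders "divided by the total number of patients in the All Treated Analysis Set".

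No section gives the number of responders needed for success, or the formula or software behind 34 and 85%. The Protocol's reference list includes sample size tables for exact single-stage phase II designs, but 11.1 does not cite them.

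**The concern.** All the inputs to the power claim stand in one sentence, so it can be checked without any outside assumption. When checked, the exact test does not give 85% at 34.

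This is the trial's only powered claim, and p-values are reserved for this endpoint. The error understates the planned chance of missing a true 65% response rate: it is 17.4% (100% − 82.6%), not 15%. The sentence also calls 34 the minimum needed for 85%, and for the named test that is not so. Stating the critical count would have shown the mismatch.

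**Working it through.** **Inputs.** Null rate p0 = 0.40 (Protocol 11.3.1, SAP 8.1). Assumed rate p1 = 0.65, one-sided alpha 0.025, n = 34 treated, stated power 85%, exact binomial test (Protocol 11.1, SAP 3.2).

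**Step 1: reproduce the stated pair.** The uncorrected normal approximation with null and alternative variances gives

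n = [(1.960·√(0.40·0.60) + 1.036·√(0.65·0.35)) / (0.65 − 0.40)]² = [(1.960·√0.24 + 1.036·√0.2275) / 0.25]² = 33.85, rounded up to 34.

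Its power at 34 is Φ[(0.25·√34 − 1.960·√0.24) / √0.2275] = 0.8516, or 85.2%. Both stated figures come out. Other common approximations do not give 34: alternative variance only 32.7 (33), null variance only 34.5 (35), arcsine 35.1 (36), continuity-corrected 37.7 (38). That the normal approximation was used is therefore an inference from the arithmetic.

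**Step 2: the exact test at n = 34.** The cut-off is the smallest r with P(X ≥ r | n, 0.40) ≤ 0.025.

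- P(X ≥ 19 | 34, 0.40) = 0.0444, too large.
- P(X ≥ 20 | 34, 0.40) = 0.0205, so the test rejects at 20 or more.
- Power = P(X ≥ 20 | 34, 0.65) = 0.8257, or 82.6%.

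As a check on the tail calculation, P(X ≥ 22 | 34, 0.40) = 0.0031. This matches the p-value that the Protocol's clinical background reports for the previous study, where 64.7% of 34 patients (22/34) responded against a 40% null.

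**Step 3: other readings of the test.** The mid-p test and the two-sided exact test at 0.05 both keep the cut-off at 20, so power stays at 82.6%. A one-sided level of 0.05 would give a cut-off of 19 and 90.1% power, and would need only 28 patients for 85%. None of these readings gives 34 with 85%.

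**Step 4: exact power over the planned range.**

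| Treated | Reject at ≥ | Actual alpha | Power at 65% |
|---|---|---|---|
| 34 | 20 | 0.0205 | 0.8257 |
| 35 | 21 | 0.0133 | 0.7891 |
| 36 | 21 | 0.0200 | 0.8446 |
| 37 | 22 | 0.0131 | 0.8113 |
| 38 | 22 | 0.0195 | 0.8613 |
| 39 | 23 | 0.0128 | 0.8311 |
| 40 | 23 | 0.0189 | 0.8761 |
| 41 | 24 | 0.0126 | 0.8487 |

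The smallest n reaching 85% is 38. Power is saw-toothed because the cut-off moves in whole patients, so 39 and 41 fall below 85% again.

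**Step 5: the cap of 41 (side point).** 34 × 1.2 = 40.8, rounded up to 41. To keep 34 after losing 20% of those enrolled needs 34 / 0.8 = 42.5, so 43. With 41 enrolled, 34 remain after 41 − 34 = 7 losses, and 7/41 = 17.1%.

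**The case against.** The best case for leaving the text alone is that the gap is small and changes nothing downstream. It is 2.4 points at the minimum number. Type I error is held (2.05% against 2.5%). The plan allows up to 41 patients, and if all were treated the power would be 84.9%, which rounds to 85%. All of that stands, and it limits the weight of the point. It does not rescue the sentence, which attaches 85% to 34 patients and to the exact test.

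Four stronger readings are tempting, and the documents do not support them.

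- *The sponsor used a normal approximation.* A reader might infer this from step 1. No document names a formula, so the match shows consistency, not origin.
- *Enrolment may stop early, leaving far fewer than 34 and much lower power.* A reader might infer this from the statement that enrolment "will continue until emapalumab is commercially available for a given indication, or until sample size is reached, whichever comes first". In Protocol section 4 the subject of that sentence is only patients who failed previous conventional therapy. The synopsis wording is broader, but both texts conclude only that US enrolment is limited to treatment-naïve patients. They narrow who may enter; they do not plan for fewer than 34. Power at some much smaller number would be an illustration with no basis in the documents.
- *The cap of 41 weakens the primary test.* The primary denominator counts everyone given any part of an infusion, so a loss after dosing leaves it unchanged. Only patients lost before dosing reduce it, and the documents give no rate for that. Protocol 11.4.1 also provides for recruiting additional patients when someone is "withdrawn from the study for reasons other than safety or lack of efficacy", with the aim of at least 34. That policy does not cover every kind of loss, but a two-patient difference (43 against 41) has no demonstrated effect on the powered test.
- *The trial needs 38 patients.* It would for 85% exact power, but nothing in the documents makes 82.6% inadequate. An accurate statement is enough.

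**Conclusion.** Wrong as written. For the test, rates and level that the plan itself states, 34 treated patients give 82.6% exact power with rejection at 20 or more responders and an actual one-sided alpha of 2.05%. The overstatement is 2.4 percentage points. For at least 85%, the minimum is 38. Between 34 and 41 treated patients, exact power ranges from 78.9% (35) to 87.6% (40), and only 38 and 40 reach 85%.

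The result rests only on the documents' own inputs and the usual exact rule (the smallest cut-off with a tail probability of at most 0.025). The explanation through the normal approximation is an inference and the conclusion does not depend on it. The validity of the primary analysis is not in question. The cap of 41 is a minor matter of description: it covers a loss of about 17%, not 20%, and bears on the primary test only for patients lost before dosing.

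**What to change.** Change the wording in Protocol 11.1, the Protocol synopsis and SAP 3.2. Replace the 85% power claim with: *34 treated patients give 82.6% exact power, rejecting the null hypothesis at 20 or more responders out of 34 (actual one-sided alpha 2.05%)*.

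Optionally, add that exact power varies with the number treated, from 78.9% to 87.6% for 34 to 41 patients.

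As a minor clarification, say that 41 is 34 plus 20% of 34 and preserves 34 patients for up to 7 losses (17%), and that only losses before dosing reduce the primary denominator.

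The cost is small: no added patients, and no change to the test, its level or the analysis sets. The stated power becomes slightly less favourable. Two of the three places are in the Protocol, so the amendment would have to be assessed under Protocol 12.6 for whether formal approval is needed.
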